 Category Continuing 8c Review - Data Analysis	Continuing review of research previously approved by the convened IRB where the remaining research activities are limited to data analysis.
 Category Continuing 9 Review - No Risk	Continuing review of research, not conducted under an investigational new drug application or investigational device exemption where categories 2-8 do not apply but the IRB has determined at a convened meeting that the research involves no greater than minimal risk and no additional risks have been identified.

ID: MS8_HM20006941

View: SF - Research Description

Research Description

1. * Describe the study hypothesis and/or research questions. Use lay language whenever possible.

We will conduct a longitudinal pilot trial of the 12-week "MOMS intervention" (Mindfulness of Movement and Symptoms) in pregnant women with current depressive symptoms (n=41) with the primary aim of determining the feasibility and acceptability of this SM intervention. This interdisciplinary team of nurse scientists, psychologists, a statistical genetics methodologist, and a biostatistician is well positioned to use innovative biobehavioral measures (maternal psychobehavioral measures; genome-wide and gene-specific epigenetic patterns; baby♦'s birth weight) to evaluate the preliminary effects of the MOMP intervention. We will compare these data with recently collected archival comparison group data from an existing study (NIMHD 2P60MD002256; PI: [name]) that has examined the same longitudinal psychobehavioral and epigenetic measures, and baby♦'s birth weight, at the same timepoints in pregnant women with depressive symptoms who are receiving UC (n=40) and women without depressive symptoms (n=40).

2. * Describe the study's specific aims or goals. Use lay language whenever possible.

This pilot study has the following specific aims:

1. Evaluate the feasibility and acceptability of the MOMP intervention for pregnant women with depressive symptoms by: (a) exploring recruitment, retention, adherence, and satisfaction data during the 12-week prenatal intervention and at a 6-week postpartum visit; and (b) evaluating participants♦' experiences after the intervention with a semi-structured interview at the postpartum visit.

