Because untreated or under-treated depressive symptoms are associated with a variety of poor maternal-child outcomes (e.g., poor maternal health behaviors, suicide, poor maternal-fetal/child attachment, intrauterine growth restriction, adult-onset chronic illnesses in offspring), a focus on the symptom experience and adequate symptom management during pregnancy is an urgent clinical and research priority.^{3,17}

Women with chronic depressive symptoms during pregnancy are in great need of safe, inexpensive, nonpharmacologic, accessible therapies to address current depressive symptoms and prevent future recurrences. Physical activity and nurse-partnered interventions which empower women to self-manage symptoms are in demand either as an adjunct or an alternative to UC, in order to enhance well-being and reduce symptom burden during pregnancy and into the postpartum period. In this project, we will pilot test a self-management (SM) intervention entitled ♦Mindfulness of Movement and Symptoms♦ (MOMS) which has three key components: (1) a nurse-participant partnership to foster awareness of depressive symptoms and goal-setting for symptom management through motivational interviewing; (2) mindful physical activity (PA) through group prenatal yoga; and (3) self-directed home mindful PA. This approach builds on our preliminary work for this application demonstrating that pregnant women prefer to play an active role in symptom management and that they view yoga as an accessible, preferred form of mindful PA.¹⁸⁻²⁰

4. * Describe the proposed research using language understandable to those IRB committee members whose expertise is not scientific. The description must include:

- **A statement explaining the study design**
- **A detailed description of all the procedures that will be followed to carry out the study, preferably in sequential order**
- **A description of all research measures/tests/interventions that will be used (if applicable)**
- **A detailed description or list of all secondary data elements and/or secondary specimens that will be obtained and how they will be used (if applicable)**

See the help text for additional guidance.

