Weekly contact by study staff (phone or email per participants' choice): Study staff will maintain regular contacts in the mode of participants' choice during the 12 weeks of the intervention. This is intended to help with retention as well as monitoring for adverse events. Study staff will collect data about minutes of physical activity during these weekly phone contacts. No survey or other data will be collected during this contacts, unless a participant verbalizes a physical or psychological adverse event.

Study Visit #7 (Intervention Week 6): Participants will be asked to complete questionnaires at the midpoint of the 12-week intervention at home electronically (if they have computer access at home) or in paper/pencil form (for those without sufficient comfort levels or access to a computer~~to~~RA will pick them up at participants~~to~~ next class).

Study Visit #14-- Last visit during pregnancy: Participants will complete another set of questionnaires electronically or in paper/pencil format. A blood sample will also be collected (8 ml blood by venipuncture in 2 EDTA [purple top] tubes).

Study Visit #15-- Postpartum Visit/Interview Session: Each participant will meet with study staff (RA, PD, and/or PI) to complete the questionnaires and participate in a semi-structured interview. Specific questions for this semi-structured interview are found in the Study Interview Guides/Scripts document. This interview will be audiotaped (and later transcribed).

Note: if a participant chooses to withdraw from the study, they will be given the opportunity to give their reasonings for withdrawal in the form of a short interview with research staff.

**** For Addendum Feb 2018: "Long-Term Follow-Up" study visit:** participants who "opted-in" to being contacted for future study will be contacted via email and/or phone about answering survey questions. Participants will give consent via REDCap (or in rare instances, may choose paper & pencil, which will be completed in-person with the research nurse) and will answer survey questions, using the same measures that have been used at previous study visits.

STUDY MEASURES

** SEE TABLE 1. STUDY MEASURES BY TIMEPOINTS

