
Objective Measures: (a) **Epigenetic (DNAm):** Peripheral blood specimens will be collected at baseline (gestation 12-22 weeks) and intervention week 12 (gestation of 24-34 weeks), as summarized in Table 1. The PD and/or RAs will arrange to meet participants to collect the blood and transport samples to the VCU School of Nursing's lab for DNA extraction.

Samples will be shipped to HudsonAlpha for DNA methylation assays. HudsonAlpha will use the following procedures for DNA methylation: genome-wide methylation patterns will be determined using the 450K HumanMethylation Chip (Illumina) according to the vendor's protocol. Briefly, DNA will be extracted from the blood samples using standard techniques (Puregene Isolation Kit; Qiagen). Following bisulfite conversion of the DNA, the methylation patterns of the 485,764 targets (including CpG islands, shores, open sea) interrogated in the 450K array will be determined. To verify the results of the 450K array for targeted regions of interest, single loci methylation-sensitive studies of bisulfite converted DNA will be conducted using standard methods.²⁰⁵ Gene-specific patterns of candidate genes chosen a priori will be closely examined. All samples will be coded prior to deliver to the testing labs. As methylation patterns vary from tissue to tissue, one concern is if the patterns present in white blood cells are reflective of the relevant cumulative epigenetic changes

involved in chronic depressive symptoms. Skepticism regarding the utility of blood for the assessment of conditions having brain/nervous system components has recently been diminished by the observation that comparable DNAm changes induced by environmental/social events occur in multiple tissues.⁷⁵ Based on these findings, Szyf²⁰⁶ noted that the results of recent investigations demonstrate that it is feasible to study behaviorally related DNA methylation signatures in peripheral cells²⁰⁶ (p.334). Given this supporting data, as well as the practical need to collect a minimally invasive specimen for study in this pregnant population, peripheral blood will be used to assess DNAm patterns. (b) Birth weight: At the postpartum visit, mothers will be asked to report the baby²⁰⁶s birth weight.

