above. Findings from this specific aim will provide important preliminary data for future explorations of epigenetic factors involved in treatment response.³⁹

RETENTION AND ADVERSE EVENT MONITORING:

Participants will be contacted weekly by the PD or RA (in the format preferred by participant: phone, text, email) to enhance retention, monitor for any adverse events, and schedule study visits. No data will be collected during these contacts. Participants will be asked if they have any physical or psychological concerns that have arisen and action will be taken if necessary. See protocol for adverse event monitoring in uploaded documents.

5. Upload any supporting tables or documents (e.g. protocol documents, figures/tables, data collection forms, study communications/reminders):

ID: MS8_HM20006941

View: SF - Study Activities

Study Activities

1. * Select which study type best describes the majority of the study. Your response will help determine which IRB panel should review this:

- Bio-Medical
-
- Qualitative - Social/Behavioral/Education (SBE)
-
- Quantitative - SBE
-
- Mixed Method - SBE
-
- Mixed Method - Biomedical
-

2. * This study will involve (check all that apply):

- procedures such as surveys, interviews, field studies, focus groups, educational tests, deception, psycho-physiological testing, any other similar data collection
-
- secondary data analysis: procedures such as analysis of information collected for non-research purposes (includes both retrospective and prospectively collected information), or analysis of data previously collected for a prior research study
- drugs, devices, experimental interventions, biohazards, radiation, other medical or surgical procedures
-

ID: MS8_HM20006941

View: SF - Bio-Med Project Details

Bio-Med Project Details

1. * Select all details that apply:

- Drugs, Biologics, Supplements, and/or Other Compounds
-
- Placebo
-
- Washout Period
-

Device Evaluation

Bio-Hazards, Other Toxins, Recombinant DNA/Gene Transfer

Radiation Exposure and/or Scans involving radiation (PET, MRA)

Stem Cells

Expanded Access - Treatment Use of an Investigational Product

Other Medical or Surgical Procedures

Protected Health Information (PHI)

ID: MS8_HM20006941

View: SF - Social/Behavioral Project Details

Social/Behavioral Project Details

1. * Select all that apply to this study:

Analysis of Information Originally Collected for Non-Research Purposes

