Blood samples will be collected by a trained phlebotomist (PD and/or RA). 8ml blood will be collected by venipuncture in 2 EDTA [purple top] tubes at two points in the study: study visit #1 and study visit #14. The PD and/or RAs will arrange to meet participants to collect the blood in a private, quiet location (most likely research space on the 4th floor of the VCU School of Nursing) and transport samples to the VCU School of Nursing's lab for DNA extraction. Samples will be shipped to HudsonAlpha for DNA methylation assays.

4. * Will Genetic Testing be conducted on any of the samples:

Yes

No

5. * Will any of the samples be used for a pregnancy test:

Yes

No

6. If yes, describe how positive pregnancy results will be communicated to the participant, particularly if minors are involved:

7. * Will any of the samples be used to screen or document alcohol or illicit drug use:

Yes

No

8. * I am aware that I may need to establish a research account with VCUHS Department of Pathology for specimen processing:

Yes

No

ID: MS8_HM20006941

[View: SF - Blood Details](#)

Blood Details

1. * Select all of the methods of sample collection that will be utilized in this study:

Individual Needle Stick(s)

Indwelling Catheter Placed Solely for This Study

Indwelling Catheter Placed for Other Reason(s)

Blood Collected at the Same Time as Non-Research Blood Collection(s)

Unused Blood Originally Drawn for Clinical Purposes

Other

ID: MS8_HM20006941

[View: SF - HIPAA](#)

HIPAA

1. * Describe the protected health information that will be obtained or used in this research:

Participants will self-report past and current medical history, current medications, pregnancy information (gestational age), depressive and other symptoms.

2. * Describe the source(s) of the protected health information:

participant self-report

3. * Explain how the PHI collected or used in this research is the minimum necessary to accomplish this research:

This is the minimum necessary for us to conduct the study and answer our research questions

4. * Select all pathways this research will employ to use or access PHI:

De-Identified Data (none of the 18 identifiers are recorded or associated with the research data)

Limited Data Set

Waiver of Authorization

Partial Waiver of Authorization

Signed Authorization Combined with Consent Form

Signed Authorization as Stand-Alone Form

Partial Waiver of Authorization

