This pilot study is intended to provide effect size estimates to inform future studies, rather than having sufficient power to address intervention effectiveness. With regards to Specific Aim 2, the proposed sample size is expected to yield reasonably stable preliminary data, based on van Belle's assertion that a minimum of 12 observations should be used to calculate confidence intervals based on the t-statistic with $n - 1$ degrees of freedom. This rule is based on the fact that the half-width confidence interval for the mean decreases rapidly up to $n = 12$, at which point the decrease is less dramatic and the half-width curve begins to asymptotically decrease.¹⁷¹ Our previous experience with individuals with depressive symptoms in research studies has yielded attrition rates between 20-40%, hence our target sample size of 40 women to participate in the intervention will be sufficient to estimate group means and variances as well as within subject correlations to estimate effect sizes to guide the design of future studies. With regards to Specific Aim 3, the total sample size is $N=120$, which includes the intervention group ($n=40$), the positive comparison group ($n=40$), and the negative comparison group ($n=40$). This sample size is very appropriate, given that it is of greater magnitude to other related epigenetic studies. For example, Guintivano and colleagues identified DNA methylation patterns which successfully predicted the onset of postpartum depression in $n=93$ pregnant women;¹⁷⁰ Yehuda and colleagues identified DNA methylation differences between responders and non-responders to a psychological intervention in combat veterans with post-traumatic stress disorder in a sample size of $n=16.77$.

4. * List the study inclusion criteria:

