This study will enroll pregnant women who have depression symptoms. Although pregnant women are considered to be a complex or vulnerable population,¹ the National Institutes of Health have stated an objective to encourage research on safe and effective interventions for conditions affecting pregnant women.¹ The self-management intervention is expected to carry less than minimal risk for pregnant participants and no risk to the fetus. No data will be directly collected from the fetus/child; mothers will report the baby's birth weight at the postpartum visit, hence the child is not considered to be a research participant. This study is in compliance with all expectations of research outlined in ²46.46.204 (Additional Protections for Pregnant Women, Human Fetuses and Neonates Involved in Research) of the U.S. Department of Health and Human Services Policy for Protection of Human Research Subjects.²

[name] (PI) has pilot tested the use of a manualized yoga-based PA intervention in a sample of diverse women with moderate-to-severe depressive symptoms; results supported feasibility, acceptability, and short- and long-term

effectiveness.^{18,19,155} We have built upon that study to develop the MOMS intervention by integrating feedback from participants regarding: the length of intervention (we have lengthened the group-based classes from 8 to 12 weeks);¹⁸ and the need for specific knowledge about depressive symptoms and goal-setting to enhance long-term adherence to PA (we have added the nurse-participant partnership and self-guided home PA aspects).¹⁵⁵ We have adapted the group yoga class manual for pregnancy for the MOMS intervention. The PI has recently completed focus groups with pregnant women and new mothers, learning that many women do not receive encouragement from their obstetricians to engage in PA.^{20,137} Moreover, the majority expressed interest in partnering with a healthcare professional to learn about their depressive symptoms and in engaging yoga-based PA as a therapeutic modality for mental and physical well-being.^{20,137} Drs. [name], [name] (Co-I), and [name] (Co-I) have relevant experience with the conduct of randomized controlled trials on health behavior, motivational interviewing, and PA interventions in various populations, including racially and socioeconomically diverse women of child-bearing age, such as those included in this application.¹⁵⁶⁻¹⁵⁹

2. * Select the condition that is applicable to this study [45 CFR 46.204(b)]:

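### Birth weight has one stated collection point, the 6-week postpartum visit, and no delivery date is named, so values may be missing and a weight difference cannot be separated from delivery timing

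*Combined protocol and SAP*

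**What the plan says.** Specific Aim 2 (Research Description, item 2) lists birth weight among the outcomes to be compared with archival usual-care data to estimate effect sizes. The Data Analysis Plan for Aim 2 makes PHQ-9 the primary variable and plans correlations between birth weight and group. No gestational-age term is mentioned.

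On collection, Objective Measures (b) (Research Description, item 4) says "At the postpartum visit, mothers will be asked to report the baby"'s birth weight and names nothing else. The section on Pregnant Women or Fetuses repeats this in items 1 and 3: mothers report "birth weight at the postpartum visit, hence the child is not considered to be a research participant". Aim 1 places the visit "at a 6-week postpartum visit", and the Study Visit #15 paragraph describes a meeting with study staff.

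On other sources, HIPAA item 1 states: "Participants will self-report past and current medical history, current medications, pregnancy information (gestational age), depressive and other symptoms". Item 2 gives participant self-report as the source. The Partial Waiver section allows the medical record to be viewed for eligibility only, with nothing retained.

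On dropouts, the Aim 2 analysis text keeps their data under intent-to-treat principles. The Feasibility and Acceptability Measures offer them an open-ended interview about leaving. Birth weight is not mentioned there.

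On other contacts, the Retention section says "Participants will be contacted weekly by the PD or RA (in the format preferred by participant: phone, text, email"), and adds that these contacts collect no data. The Weekly contact paragraph limits them to the 12 intervention weeks and allows only activity minutes and adverse events to be recorded. In the long-term follow-up, women who opted in "will answer survey questions, using the same measures that have been used at previous study visits".

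**The concern.** Birth weight is fixed at delivery and needs no visit to obtain. Tying it to attendance some six weeks later makes an outcome that a single question could supply depend on a woman turning up.

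Attendance may be related to the outcome. Under the withdrawal criteria (Risks section, item 8), preterm labor or delivery is a ground for withdrawal when the woman's provider also advises her to stop yoga. A woman who leaves for that reason may lose the only stated point at which her baby's weight is asked.

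The second part is interpretation. The comparison groups are archival and matched on age and race only, so nothing in the design balances delivery timing. A baby can weigh less because it was born earlier or because it grew less. Weight alone does not separate the two, and the pilot's effect-size estimate for birth weight would carry that ambiguity into later planning.

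**Working it through.** **Stated figure.** The plan contains no power or sample-size calculation for birth weight, so there is no derived figure to reproduce. The intervention target of 40 (Study Population, item 3; 41 in the inclusion criteria) rests on a rule of at least 12 observations and on earlier experience that "has yielded attrition rates between 20-40" percent. The totals agree: 3 × 40 = 120, and 41 + 40 + 40 = 121.

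**Birth weights at risk.** Assume that non-attendance at Visit 15 equals that earlier attrition.
- Missing: 41 × 0.20 = 8.2 and 41 × 0.40 = 16.4, so about 8-16.
- Observed: 41 × 0.80 = 32.8 and 41 × 0.60 = 24.6, so about 25-33.

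Both ends stay above the plan's minimum of 12, so its size rule is met.

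**Precision.** In SD units, the 95% half-width for MOMS against the positive comparison group is t(0.975, n1 + n2 − 2) × √(1/n1 + 1/n2). With the archive assumed complete at n2 = 40:

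| MOMS birth weights | Half-width (SD) |
|---|---|
| 40 | 0.445 |
| 32 (20% missing of 40) | 0.473 |
| 24 (40% missing of 40) | 0.516 |

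The loss of precision is modest.

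**Selection.** If a share f is missing and attenders' babies differ in mean from non-attenders' by D, the complete-case mean of the group is off by f × D. D is not in the documents. For an assumed D of 0.25-1.0 SD:
- f = 0.20: 0.20 × 0.25 = 0.05 to 0.20 × 1.0 = 0.20 SD
- f = 0.40: 0.40 × 0.25 = 0.10 to 0.40 × 1.0 = 0.40 SD

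These are errors in the MOMS mean. The error in the group difference is f × D for MOMS minus f × D for the archive. With the same f and D in both, it is zero. The archive's values are not given, so neither sign nor size follows.

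**Delivery timing.** If birth weight and gestation at birth correlate at r, and the groups differ by g SD in gestation, mean weight shifts by r × g SD with no difference in weight at a given gestation. For assumed r of 0.3-0.7 and g of 0.2-0.5, this runs from 0.3 × 0.2 = 0.06 to 0.7 × 0.5 = 0.35 SD. These inputs are illustrative; the documents give none.

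**Can gestation at birth be derived from what is named?** Gestation at birth = recorded gestational age + (delivery date − date of that record)/7, in weeks. The HIPAA section supplies the first term. No section shown supplies the delivery date. Counting back from a visit at about 6 weeks gives only an approximation, and nothing for women who miss the visit.

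**The case against.** The strongest reply is that this reads silence as absence. Table 1 and the Study Instruments are separate uploads, and a delivery-date item on a form cannot be excluded. The long-term survey reuses earlier measures and may already repeat birth weight. That stands: a reader might infer that birth weight is lost for every non-attender and that delivery date is never recorded, but the documents support only that neither a second route nor a delivery date is stated.

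A reader might also infer that the MOMS mean is biased upward against the archive. The Comparison Group Data paragraph calls the archive's birth weight measures identical to this study's, so similar loss there could offset part or all of it. The direction is not shown.

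Nor is growth restriction the plan's declared target. The background lists "intrauterine growth restriction" as one of several consequences of untreated symptoms, and no aim claims an effect on fetal growth. The need for gestation at birth rests on interpreting the weight comparison itself.

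The plan does help attendance: the visit is timed to the routine postpartum obstetric visit and can take place at the obstetrician's office. The 20-40% is earlier whole-study experience and may overstate absence here. The weekly contacts are also no ready-made channel. They end with the intervention, at about 24-34 weeks' gestation, and are not set up to collect this item.

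What remains is that the text promises to retain dropouts in the analysis yet gives no route to their birth weights, and names nothing that would show delivery timing.

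**Conclusion.** The point holds as a cheap, worthwhile improvement to an outcome of a feasibility pilot that is not its primary variable. One in-person visit is the only stated source of birth weight, there is no chart back-up, and no delivery date is named in the text shown. About 8-16 of 41 values would be missing if absence at Visit 15 matched earlier attrition. That is an assumption and should not be read as a forecast. Full recovery would improve precision only modestly (0.473-0.516 to 0.445 SD, taking 40 women and a complete archive), so the gain lies mainly in less possible selection and in being able to interpret a difference.

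Bias against the archive is possible, with unknown sign and size. The problem with delivery timing needs no numerical assumption: without gestation at birth, this non-randomised comparison cannot separate a weight difference from a timing difference. If the unseen forms already record a delivery date, that half is met and the body text should say so.

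**What to change.** Amend Objective Measures (b) so that birth weight and delivery date are asked of every enrolled woman who has not withdrawn her data: at Visit 15; if it is missed, by phone, text or email; and in the 10-20 month survey for opted-in women whose values are still missing.

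Bring the related text into line. The Weekly contact, Long-Term Follow-Up and Retention paragraphs need to provide for this contact, since weekly contacts stop with the intervention and currently collect no such data. Items 1 and 3 of the section on Pregnant Women or Fetuses, which tie the report to the postpartum visit, need the same change.

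Derive gestation at birth from the recorded gestational age and the delivery date. Report the number of birth weights missing, and show gestation at birth beside birth weight for each group where the archive holds it. The archive's lead is a co-investigator, so that can be checked directly.

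The cost is two questions, a few extra contacts and one table column. Women reached only at 10-20 months will answer with longer recall, and those who cannot be reached will still be missing.
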